The Effect of a Brief Intervention for Problem Gamblers - a Randomized Controlled Pilot Trial

Last updated: 20201006

Study protocol

Background

The prevalence rates for problem gambling (PG) in Sweden remains the same despite the fact that the gambling participation declines. According to the latest prevalence survey on PG in Sweden, approximately 2% of the adult Swedish population suffer from PG. Further, 5% are at risk of developing PG (1,2). PG is hallmarked by an inability to stop or reduce gambling even though it affects several life domains, such as: personal finances, family relationships, the physical and mental health and work in a negative way (3). Despite the fact that there are treatments that work, only around 5% of the individuals in need of treatment seek help within the healthcare system (1). There is also an extensive overlap between PG and especially alcohol, depression and anxiety disorders (4–6). Given the fact that few gamblers in need of treatment actually seek help within the healthcare sector, it is urgent to develop and evaluate interventions with a low threshold to participate.

Treatment outcome research

Internationally, there is a growing body of research on psychological treatments for PG. To this date, cognitive behavioural therapy (CBT) delivered face-to-face, has yielded the strongest support, but the evidence level is still considered low (7). There is also some support for brief motivational enhancement interventions, usually delivered via telephone, consisting of an initial counselling session based on Motivational Interviewing (MI) aligned with additional support consisting of written self-help material and/or booster sessions via telephone (8–10). A few studies have evaluated the effects of online CBT for problem gamblers, showing promising results (11,12). Overall, there is a growing body of evidence supporting the effects of Internet delivered CBT-interventions (13). Further research on psychological treatments for PG is needed.

Gambling helplines

A natural entry point for individuals suffering from PG in Sweden is the Swedish National Gambling Helpline, the helpline. The helpline offers anonymous support and counselling to gamblers and concerned significant others (CSOs) via telephone, chat or email. The helpline also offers online screening of gambling habits with personalised feedback, and self-directed online help. On an annual basis about 1200 gamblers and 1000 CSOs contact the helpline for counselling and support. Approximately 3500 gamblers screen their gambling habits online and 1200 registers for the self-directed online help (14).

In an international context, gambling helplines have been around for decades, but to our knowledge only one evaluation of its effectiveness has been conducted, compiled as a report to the New Zealand Ministry of Health. At the New Zealand gambling helpline, four different interventions were tested: 1) the regular counselling, 2) one MI-session, 3) one MI-session plus written self-help material, and 4) one MI-session, written self-help material and up to four booster counselling sessions. The authors were not able to show superiority of any intervention, but at a sub-group level they found that gamblers experiencing greater problem

gambling severity, greater levels of depression and anxiety and who were consuming alcohol at an "at-risk"-level benefitted from the most extensive intervention (15).

Given the fact that the Swedish gambling market has undergone a major transformation over the last decade - from being mainly a land-based market to predominantly being an online gambling market (16), and the fact that almost all Swedish citizens have access to the Internet, and the growing support for Internet delivered CBT-interventions - the natural development of offering written self-help materials and/or booster sessions in connection to an initial counselling session in a gambling helpline is to offer the extended contact as a brief online CBT-intervention. A study at the Australian gambling helpline discovered that the gamblers were primarily in need of practical tools on how to manage their gambling, rather than help enhancing their motivation to change (17). CBT provides concrete tools for changing the gambling habits.

Aims

The aim is to test the feasibility of a brief online CBT-intervention at the Swedish national gambling helpline's counselling service, more specifically: pilot-test of a short online CBT-program in connection to an initial counselling session at the gambling helpline.

Method and materials

Design

A pragmatic randomized controlled pilot trial examining feasibility of an additional brief online CBT-program in connection to an initial counselling session in the helpline. The study participants will, after an initial counselling session with the helpline, be randomized to either a brief online CBT-program or to log their gambling habits for six weeks.

Outcomes

The main outcome is feasibility of conducting the study, secondary outcomes are net losses to gambling, days gambling, problem gambling severity level, gambling urges, self-efficacy in gambling situations, psychosocial health and general social functioning.

Participants

Study participants will be recruited from the helpline's counselling service and webpage. Gamblers' scoring above 3 points on the PGSI scale are eligible for inclusion. Other inclusion criteria are:

- Aged over 18 years
- Good enough skills in the Swedish language
- Access to the Internet

Exclusion criteria are:

- Being involved in a treatment research study the previous 3 months

- Receiving other treatment for PG
- Being on a non-stable drug treatment for any psychiatric disorder
- Showing signs of severe depression

Randomization

Participants will be randomized using block randomization with varying block sizes (ranging between 2 to 8 participants per block) to ensure balanced groups.

Data collection

Data will be collected at baseline, weekly during the treatment, after the treatment, and 6 weeks after the end of treatment.

Intervention

The internet-based CBT program that is the intervention in the study is developed by the research group and is based on CBT treatment for problematic gambling (see 18). The program have elements of psycho-education, functional analysis on gambling situations, behavioural activation, reflections on thoughts about gambling and relapse prevention, and basically the same motivational increasing principals that is used in the Motivation Interviewing (MI) method. The program consists of four modules that are given during six weeks (week 1, 2, 4, and 6 after randomization). Each module has its own team with text to read and exercises. When a module is completed, the participants receive feedback from a counsellor via a messaging system in the web platform. The feedback aims to highlight and strengthen the client's self-determination and own ability to change their behaviour. In the last module, the progress made and tips for further support are summarized. Themes for the four treatment modules are as follows:

Week 1: Objective of treatment, psycho-education, functional analysis on gambling

Week 2: Functional analysis on gambling situations, thoughts on gambling and behavioral activation

Week 4: Behavioural activation and functional analysis on gambling-free activities

Week 6: Relapse plane: to maintain a gambling-free life with focus on handling risk situations and engage in gambling-free activities.

The ordinary counsellors at the helpline will be the counsellors in the study and will be educated in the CBT method before the study starts. They all have a long experience to work with persons who are problematic gamblers and they will receive continuous supervision by a certified psychologist. The written feedback given to the counsellors will be reviewed to ensure that the treatment is given according to the CBT method.

Statistical analyses plan (SAP)

Feasibility will be analysed using mainly descriptive statistics. To analyse the longitudinal data a three-level regression model will be used. The highest level in the hierarchy consists of the therapist, the second level is the client and at the lowest level are the repeated measurements made on the clients. The main outcome in the longitudinal part of the study will be net losses, and based on earlier knowledge it is known that this outcome have a distribution that is far from a normal distribution. It has a distribution with high peaks at both ends of the measured values. Therefore, the regression models used to analyse the longitudinal data will not be linear models but rather zero-inflated or alternatively hurdle models based on either a Poisson distribution or a negative binomial distribution.

Ethical considerations

Since the patient group is fairly new and society's help is limited, there is a risk that patients with too extensive need of support apply to participate in the intervention study. To make sure that no one is left without help, participants who for any reason are excluded from the study will be referred to help in their vicinity. The helpline has a record of addiction and psychiatric care to all of Sweden's municipalities and county councils.

Further, participants will be systematically followed up within the study, which enables the research group to have a constant supervision of the treatment process. Participants who are still experiencing problems after intervention termination will be referred to help in their vicinity.

Participants who end the intervention without telling, will be contacted via telephone up to 3 times to check further participation, and will, if necessary, be offered a referral to further treatment. Deviations will be reported in the participant's paper journal. Personal data will be handled according to the Swedish Data Protection Act.

In previous outcome studies participants have benefitted from the treatment they have received. It is likely to believe that those who participate in the study will benefit from the intervention. It is also likely to believe that future problem gamblers will benefit from the study.

References

1. Statens Folkhälsoinstitut. Spel om pengar och spelproblem i Sverige 2009 / 2010. Statens folkhälsoinstitut; 2010.

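### Does the plan need changing because feasibility, its main outcome, has no named measures, denominators or time points?

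*Combined protocol and SAP*

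**What the plan says.** The Aims section states "The aim is to test the feasibility of a brief online CBT-intervention", and the Outcomes section states "The main outcome is feasibility of conducting the study". Net losses, days gambling, problem severity and the other clinical measures are listed there as secondary. In the SAP, the whole provision for the main outcome is "Feasibility will be analysed using mainly descriptive statistics". The SAP then turns to the repeated measurements, for which it plans a three-level regression (therapist, client, occasion), and adds "The main outcome in the longitudinal part of the study will be net losses".

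Other sections contain material that could serve as feasibility measures, without labelling it so:

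- Participants: recruitment from the helpline's "counselling service and webpage".
- Design: clients will, "after an initial counselling session with the helpline, be randomized".
- Data collection: baseline, weekly during treatment, end of treatment, and six weeks later.
- Intervention: four modules over six weeks, and a review of written feedback.
- Ethical considerations: up to three telephone contacts for clients who stop without notice.

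The documents give no sample size, feasibility target or progression criterion.

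**The concern.** A main outcome would normally come with a definition: what is counted, out of whom, and when. Here the plan names a concept and a style of analysis. The word mainly also leaves room for some further, unnamed analysis. Completion could mean opening one module or finishing four. Retention could be taken at either post-treatment assessment. Recruitment could be set against counselling contacts or against everyone the helpline reaches. If those choices are made after the data are seen, a favourable rate can be put forward and an unfavourable one left out.

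Two further features add to the unease. The aim speaks of the intervention while the outcome speaks of conducting the study, and neither has its own measures. Net losses gets a much fuller analysis description than feasibility does, so a between-arm comparison on a secondary outcome might come to be read as the pilot's result.

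**Working it through.** The plan has no figure to reproduce: no sample size, target or expected rate is stated. The check is how far an open definition could move a reported rate, and whether ordinary reporting would hide the movement. Arm sizes, continuation and retention below are assumptions. Only the helpline counts come from the documents.

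**Modules.** Let a constant proportion c go on at each of the four modules. Then at least one module is c, all four among everyone randomised to CBT is c^4, and all four among those who finished module 1 is c^3.

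| c | At least one | All four / randomised | All four / module-1 completers | c − c^4 | c^3 − c^4 |
|---|---|---|---|---|---|
| 0.80 | 80% | 41.0% | 51.2% | 39.0 | 10.2 |
| 0.85 | 85% | 52.2% | 61.4% | 32.8 | 9.2 |
| 0.90 | 90% | 65.6% | 72.9% | 24.4 | 7.3 |

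The Wilson 95% half-width at an observed 50% is 26.3 points for 10 per arm, 16.8 for 30 and 13.4 for 50. The denominator shift (last column) is below all three. The gap between at least one and all four is above the half-width at 30 and 50 per arm. At 10 per arm it is above it for c = 0.80 and 0.85 but not for 0.90. At 30 per arm and c = 0.85 the pair is about 26/30 (70 to 95%) against 16/30 (36 to 70%). These are two nested points of one 0-to-4 distribution, not rival estimates of one quantity.

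**Retention.** Assume 70% supply data at end of treatment and 80% of those do so at follow-up. Follow-up retention is then 0.70 × 0.80 = 56% of all randomised, or 80% of end-of-treatment responders. The Wilson half-width at 70% with 60 clients is 11.3 points.

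- 70% against 80%: 10 points, below the half-width, though time point and denominator both differ.
- 70% against 56%: 14 points, same denominator, different time points.
- 56% against 80%: 24 points, same time point, different denominators.

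The last two exceed the half-width, so sampling error does not cover every choice. But all three rates follow from three counts: randomised, with data at end of treatment, and with data at follow-up. A participant flow table gives those.

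**Recruitment.** The Gambling helplines section reports: "On an annual basis about 1200 gamblers and 1000 CSOs contact the helpline for counselling and support". It continues: "Approximately 3500 gamblers screen their gambling habits online and 1200 registers for the self-directed online help". Taking the three gambler streams as fully overlapping or fully separate gives 3500 to 1200 + 3500 + 1200 = 5900. Against counselling contacts alone, the denominator ratio is 3500/1200 = 2.9 to 5900/1200 = 4.9. With an assumed 60 randomised in a year, the rate is 60/1200 = 5.0% against 60/3500 = 1.7% or 60/5900 = 1.0%. This says little about the trial's own recruitment rate. The counts are of contacts before any eligibility check, equating online screening and self-help with the webpage's recruitment reach is an assumption, and by the Design section every client is randomised after a counselling session.

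**Net losses.** Set side by side, the two descriptions agree. Outcomes lists net losses as secondary, and the SAP calls it main only within the longitudinal part. The three-level structure is stated for the longitudinal data generally. The known shape of net losses explains the zero-inflated or hurdle choice. Nothing there lets net losses decide feasibility.

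**The case for a change.** The strongest case for a change is that describing still requires saying what is described, and that this is the main outcome. The time points in Data collection are a general schedule, and the modules, feedback review and telephone contacts appear as treatment content, quality control and ethics procedure. Writing down three or four measures with denominators would be cheap and would remove the freedom to choose a headline.

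Much of that stands. No section supplies the definitions, nothing suggests they were removed from the public text, and the choice of emphasis is open until the data are seen. The 24-point retention example shows that an unconventional denominator could flatter a result if it were quoted alone.

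What does not stand is the step from missing detail to a defect. With no feasibility test and no progression threshold, there is no error rate to inflate and no pass or fail to manipulate. The worry about net losses rests on a conflict that the text does not contain. The difference between the aim and the outcome is thin, since running the programme inside the trial informs both. Nor would a full specification be free: it would need a log of screening and entry source, and a fidelity rate would need a rating procedure for each message, neither of which the documents describe.

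**Conclusion.** No change to the plan follows. The gap is one of reporting detail, which analysts of a pilot fill in the usual way: participant flow by arm, data supplied at each assessment out of all randomised, and the full distribution of modules completed. Shown together with their counts, these leave little room for a selective headline.

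In the illustrations, the module denominator alone moves the rate by 7 to 10 points, within sampling error at 10 to 50 per arm. The larger gaps (24 to 39 points between one module and four, 14 and 24 points for retention) are between labelled quantities that the same table would show. These sizes depend on assumed continuation, retention and sample sizes.

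The conclusion rests on two conditions: the pilot is reported descriptively with its counts, and no go/no-go decision hangs on an unstated threshold. The documents plan no such decision.

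### The longitudinal model of net losses gives the baseline value no stated role, which forgoes a cheap gain in precision

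*Combined protocol and SAP*

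**What the plan says.** All references are to the combined protocol and SAP.

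- **Data collection:** "Data will be collected at baseline, weekly during the treatment, after the treatment, and 6 weeks after the end of treatment". The section does not list which measures are taken at which time.
- **Design:** participants will "be randomized to either a brief online CBT-program or to log their gambling habits for six weeks".
- **Randomization:** "Participants will be randomized using block randomization with varying block sizes". No stratification is described.
- **Outcomes:** "The main outcome is feasibility of conducting the study, secondary outcomes are net losses to gambling".
- **Statistical analyses plan (SAP):** "To analyse the longitudinal data a three-level regression model will be used". Therapists are the top level, clients the second, and "at the lowest level are the repeated measurements made on the clients". Also: "The main outcome in the longitudinal part of the study will be net losses". The family is zero-inflated or hurdle, with a Poisson or negative binomial base.

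The SAP section lists no fixed effects: no arm, time, arm-by-time or baseline term, and no common-baseline constraint. It does not say whether baseline counts as one of the repeated measurements. No other section supplies these.

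**The concern.** Losses before randomisation are likely to predict losses afterwards. Blocking balances group sizes. Without stratification it balances starting losses only in expectation, so a small trial can begin with a visible difference between arms. The SAP wording allows at least four fits:

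1. Follow-up rows only, with baseline unused. Chance imbalance stays in the arm estimate.
2. Baseline as a row, separate baseline means per arm, arms contrasted at follow-up. With complete data this equals fit 1 in the linear case.
3. Baseline as a row, separate baseline means per arm, arms contrasted on change from baseline. The imbalance is over-corrected whenever the correlation is below 1.
4. Conditioning on baseline, by a covariate or by a common baseline mean.

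Fits 1 to 3 are all unbiased over repeated randomisation, but less precise than fit 4. What is at stake is a noisier arm estimate for the main longitudinal outcome, and one that moves with chance differences in starting losses.

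**Working it through.** The documents state no sample size, variance, correlation or effect size, so there is no planned figure to reproduce. **Everything below is illustrative.** It uses a linear model with equal variances at each time, and a baseline–follow-up correlation r assumed at 0.3, 0.5 and 0.7.

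**One follow-up.** Variance of the arm contrast relative to ignoring baseline:

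| Fit | Formula | r = 0.3 | r = 0.5 | r = 0.7 |
|---|---|---|---|---|
| Baseline ignored, or free arm means with follow-up contrast | 1 | 1 | 1 | 1 |
| Free arm means, change contrast | 2(1 − r) | 1.40 | 1.00 | 0.60 |
| Adjusted for baseline | 1 − r² | 0.91 | 0.75 | 0.51 |

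**Mean of several follow-ups.** Six weekly records, one after treatment and one at the later follow-up make m = 8, or m = 7 if the last weekly and post-treatment records coincide. With every pairwise correlation equal to r, V_ignored = (1 + (m − 1)r)/m, V_change = V_ignored + 1 − 2r, and V_adjusted = V_ignored − r². For m = 7 and r = 0.5:

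- V_ignored = (1 + 6 × 0.5)/7 = 0.571
- V_change = 0.571 + 1 − 1 = 0.571, ratio 1.0
- V_adjusted = 0.571 − 0.25 = 0.321, ratio 0.56

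Across r = 0.3/0.5/0.7 and m = 7 or 8, the ratios are about 2.0/1.0/0.46 for change and 0.77/0.56/0.34 adjusted.

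**Cost of estimating one covariate**, one follow-up, n per arm (assumed). The adjusted variance is multiplied by 1 + 1/(2n − 4).

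- n = 10: 1 + 1/16 = 1.06, so the adjusted values become 0.97/0.80/0.54.
- n = 30: 1 + 1/56 = 1.02, so they become 0.93/0.76/0.52.

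Setting (1 − r²)(1 + 1/(2n − 4)) = 1 gives a break-even r = √(1/(2n − 3)). This is 0.24, 0.16, 0.13 and 0.10 at 10, 20, 30 and 50 per arm. Adjustment loses only below those values.

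**Effect of a chance imbalance**, one follow-up. At 30 per arm, one standard error of the baseline difference is d = √(2/30) = 0.26 SD. The arm estimate shifts by:

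- r × d = +0.08/+0.13/+0.18 SD if baseline is ignored
- (r − 1) × d = −0.18/−0.13/−0.08 SD with a change contrast
- 0 on average if adjusted

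**The planned family.** The SAP rules out linear models, so these figures give only an order of magnitude. Simulations of the amount part of a hurdle model with a client random intercept (30 per arm, 7 follow-ups, all assumed) also favoured adjustment. Their size depended heavily on how accurately the random effect was integrated: coarse quadrature inflated the variance with baseline ignored and so overstated the gain. They also had no upper peak in the outcome, no therapist level in the fit and no zero-inflated alternative. I therefore claim only their direction. No gain is shown for the any-loss part.

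**The case against.** The strongest reply is that this is a feasibility pilot. The main outcome is feasibility, analysed mainly by description. Net losses are secondary, and no alpha, hypothesis test or efficacy decision is stated. Every number above is assumed and linear, while the planned model is neither linear nor single-part. The repeated measurements may already include baseline, and the choice between a covariate and a common-baseline row is partly taste. The remedy also presumes that net losses are recorded at baseline, which the Data collection section implies but does not list.

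Most of this stands, and it limits the importance and the size that can be claimed. It does not remove the point. Even if baseline is a row, the SAP does not say whether the arms share a baseline mean, and that separates the more precise fit from the less precise ones.

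A reader might infer that the arm comparison is biased, or that leaving the contrast open inflates false positives. The documents do not support the first: allocation is random, so the imbalance is chance. On the second, no test or error rate is stated to inflate, so the unnamed contrast is missing detail to be settled in the same edit, not a demonstrated error.

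**Conclusion.** The point holds as a cheap improvement of low importance. The longitudinal model of net losses has no stated baseline covariate and no common-baseline constraint, and fits the wording allows are less precise than conditioning on baseline. In the linear one-follow-up case the variance saved relative to ignoring baseline is 9%, 25% or 49% at r = 0.3, 0.5 or 0.7. A change contrast is worse than ignoring baseline at 0.3, equal at 0.5 and better at 0.7, but never better than adjustment before the small cost of the covariate.

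This rests on assumed correlations, equal variances, complete data and baseline measurement of net losses. A reader might carry these percentages over to the hurdle or zero-inflated model. They should not be: for the amount part only the direction is supported, and at low correlation the gain may be negligible. Nor does the point touch the feasibility conclusions.

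**What to change.** First confirm that net losses are measured at baseline. Then add one or two sentences to the SAP section that choose one of these:

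- **Covariate:** take the post-baseline measurements as the outcome rows and enter baseline net losses in the amount part, on a scale that copes with wins and zeros, for example log(1 + max(loss, 0)) plus an any-loss indicator. A baseline term in the any-loss part is optional.
- **Common baseline:** keep baseline as an outcome row with the arms constrained to the same baseline mean, and add a time term or offset if its recall window differs from the weekly one.

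In the same place, name the one main arm contrast: its time point or average over follow-up, and whether it is read from the any-loss part, the amount part or the combined mean. The amount part alone is restricted to records with a loss, which is itself determined after randomisation, so this choice should be explicit.

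No new data are needed if baseline losses are recorded. The price is one or two extra parameters in a small model: in the linear case about 6% of variance per covariate at 10 per arm and 2% at 30, before any gain, with a net loss only at very low correlation.

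### The SAP expects net losses to peak at both ends of the recorded range, but the planned models have a separate component only for zeros, so the upper peak is not modelled

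*Combined protocol and SAP*

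**What the plan says.** The Outcomes section puts feasibility first and net losses second: "The main outcome is feasibility of conducting the study, secondary outcomes are net losses to gambling". Within the repeated-measures analysis, however, net losses lead: "The main outcome in the longitudinal part of the study will be net losses".

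The SAP section plans a hierarchy of therapist, client and repeated measurement ("To analyse the longitudinal data a three-level regression model will be used"). It then describes the outcome's shape, which it attributes to earlier knowledge: "It has a distribution with high peaks at both ends of the measured values". The next sentence presents the model choice as following from that shape. The models "will not be linear models but rather zero-inflated or alternatively hurdle models", with the base left open between Poisson and negative binomial.

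The documents do not say how net losses are entered, whether there is a maximum or top category, whether the lower end is zero, or how a net win is coded. They give no censoring rule and no sensitivity analysis for the upper end.

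**The concern.** The plan describes two features of the distribution and picks a model family that addresses one. Zero-inflated and hurdle models both treat zeros separately. Above zero, each uses an ordinary Poisson or negative binomial shape, which has no term for a mass of records at the highest value.

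The comparison at stake is CBT against logging of gambling habits, on the amount lost. If the upper peak arises because heavy losses are recorded at a maximum, the model reads those records as losses of exactly that maximum. Reductions that stay above the maximum then disappear, and the arm with larger losses is truncated more. If the upper peak consists of real high losses, nothing is hidden, but a single count distribution may describe the positive amounts badly, and the precision it reports may be wrong.

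**Working it through.** **No figure to reproduce.** The documents give no sample size, effect size, spread, share of records at either end or maximum loss. Every number below is therefore an assumption or follows from one.

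**Step 1. Shape against model**

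| Feature stated in the SAP | Part of the planned model that addresses it |
|---|---|
| Peak at the lower end | Zero component, provided the lower end is zero |
| Peak at the upper end | None |

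The mismatch needs no arithmetic.

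**Step 2. If the upper peak is a ceiling.** Assume positive losses X are log-normal with log-scale mean μ and SD σ, control median 1 (μ = 0) and CBT median 0.60 (μ = ln 0.60). The true ratio of means is then 0.60. Put the cap c at the control quantile that leaves a share q of control loss records at the cap. The capped mean is

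E[min(X, c)] = exp(μ + σ²/2) · Φ((ln c − μ − σ²)/σ) + c · [1 − Φ((ln c − μ)/σ)].

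Worked case, σ = 1.2 and q = 20%: c = exp(1.2 × 0.8416) = 2.745.

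- Control: 2.054 × 0.360 + 2.745 × 0.200 = 1.289
- CBT: 1.233 × 0.527 + 2.745 × 0.1025 = 0.931
- Ratio: 0.931 / 1.289 = 0.72

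Capped ratio of means over the assumed range (true value 0.60):

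| σ | 10% of controls at cap | 20% | 30% |
|---|---|---|---|
| 1.0 | 0.66 (0.665) | 0.71 | 0.74 |
| 1.2 | 0.68 | 0.72 | 0.76 |
| 1.5 | 0.70 | 0.75 | 0.78 |

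A zero-truncated negative binomial (the positive part of a hurdle model) fitted to simulated data from the worked case also gave 0.72. It placed 0.5% of control loss records at the cap, where 20% were observed.

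The direction does not depend on the log-normal choice. With negative binomial losses (mean 20, size 1, true ratio 0.70, 100,000 per arm before zeros are dropped, no clustering), the same model gave:

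| Control losers at cap | none | 5% | 10% | 20% | 30% | 40% |
|---|---|---|---|---|---|---|
| Fitted ratio | 0.70 | 0.73 | 0.75 | 0.79 | 0.83 | 0.86 |

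**Step 3. If the upper peak is real high losses.** The negative binomial set-up is the same, with no cap, but 20% of control losers belong to a cluster of real losses near 100 units. With a ratio of 0.70 for the remaining losers:

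| CBT losers in the cluster | 20% | 14% | 10% | 5% |
|---|---|---|---|---|
| True ratio of means | 0.874 | 0.727 | 0.639 | 0.526 |
| Fitted ratio | 0.867 | 0.713 | 0.621 | 0.505 |

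The largest gap is 0.526 − 0.505 = 0.021, and every gap is away from 1. There is no shrinkage here. The expectation of poor fit and doubtful standard errors is reasoning from the shape: standard errors were not simulated, and the Poisson base was not fitted. The Poisson raises more concern because it ties the variance to the mean, which two separated peaks would breach strongly.

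**Step 4. Does censoring help under a ceiling?** With negative binomial losses and a true ratio of 0.60, about 10%, 21% and 31% of controls at the cap gave fitted ratios of 0.66, 0.71 and 0.75. Treating records at the cap as right-censored recovered 0.60 each time. In the log-normal worked case, censoring moved 0.72 to 0.64. The uncapped fit gave 0.59, so most of the remaining gap is the cost of a wrong distribution combined with a cap. Removing the cap is better than modelling it.

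**The case against.** The strongest reply is that no ceiling is documented. The description of the shape rests on earlier data and does not describe this trial's form. It may be loose wording for many zeros plus a long right tail, for which a zero-inflated or hurdle negative binomial is a conventional choice. Net losses can also be negative when a person wins, so even the lower peak being at zero is an inference. The field may already be an open amount; the upper peak would then be real, and censoring would be wrong.

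Most of this stands. A reader might infer that the plan will understate the CBT effect, for example reporting a true 40% reduction as 28% (1 − 0.72). The documents do not support that as a finding. It requires a cap they never mention and a capped share they never give, and Step 3 shows no shrinkage without a cap. Nor do they support the inference that a biased estimate would carry into a later trial, since none is described.

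Pilot noise matters too. With an assumed 40 independent positive records per arm, σ = 1.2 and 20% capped, fitted ratios ranged from about 0.5 to 1.0 across simulated sets. A shift of 0.12 (0.72 − 0.60) is small beside that.

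The reply does not remove the mismatch. Read as written, the shape has two peaks, the model addresses one, and nothing elsewhere in the documents covers the other.

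**Conclusion.** The concern holds in conditional form. The stated reason for the model family does not cover the upper peak that the plan itself expects.

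- **If that peak is a recording ceiling:** the ratio for amount lost is biased towards no effect, about 0.67 to 0.78 for an assumed true 0.60, with log-SD 1.0 to 1.5 and 10% to 30% of control loss records capped.
- **If it is real high losses:** the mean ratio is nearly unbiased, within about 0.02 under the assumptions of Step 3. The risk is then poor fit and unreliable standard errors, greater with a Poisson base.

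The wording about the ends of what was measured makes a ceiling plausible, because money lost has no natural upper limit, but it does not establish one. The simulations ignore therapist and client clustering, so they show direction and rough size only. The matter is worth correcting but limited in weight: net losses are a secondary outcome, and the main outcome, feasibility, is analysed mainly descriptively and is unaffected.

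**What to change.** 1. Record net losses at every assessment as an open numeric amount, with no top category or maximum entry, and say so in the plan.
2. If a maximum must stay, treat records at it as right-censored in the positive part of the hurdle model, and report the share at the maximum by arm and time point.
3. If there is no cap, use the negative binomial rather than the Poisson base, with robust standard errors at cluster level. Add a sensitivity analysis with a heavier-tailed or mixture distribution for the positive amounts.
4. Reword the sentence that derives the model from the two-peaked shape, so that the zero component is justified by the zeros alone and the upper end has its own stated handling.

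The cost is a form setting or a censoring option, a few SAP sentences, one extra analysis, and some extreme values to check if the field is open.
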